7.12.2 Clinical Laboratory Evaluations

For the purposes of summarization in both the tables and listings, all laboratory values will be converted to standardized units. If a lab value is reported using a non-numeric qualifier (eg, less than (<) a certain value, or greater than (>) a certain value), the given numeric value will be used in the summary statistics, ignoring the non-numeric qualifier.

If a patient has repeated laboratory values for a given time point, the value from the last evaluation will be used. Laboratory test results will be summarized according to the scheduled sample collection time point. Change from baseline will be presented. Scheduled laboratory along with unscheduled lab test results will be listed.

Lab parameters to be analyzed are as follows:

- Hematology: hemoglobin, hematocrit, activated partial thromboplastin time (aPTT), platelet count, white blood cell (WBC) count, WBC differential (basophils, eosinophils, lymphocytes, monocytes, neutrophils), prothrombin time (PT)
- Chemistry: albumin, alanine aminotransferase (ALT), alkaline phosphatase, aspartate aminotransferase (AST), bilirubin (total), blood urea nitrogen, calcium, chloride, creatinine, glucose (non-fasting), HCO₃ or CO₂, LDH, phosphate, potassium, sodium, standard C-reactive protein, urate or uric acid

- Urinalysis: protein, glucose, nitrite, occult blood, specific gravity, pH, bilirubin, ketones, turbidity and color, leukocytes, urobilinogen
- Immunosafety markers: thyroid-stimulating hormone (TSH), free thyroxine (T4), cortisol (morning preferred)

If GFR is to be estimated, the MDRD or CKD-EPI equations shall be used. References are specified in Section 9.3.13.1 of Protocol Amendment 3.

Whenever available, laboratory values will be assigned toxicity grades using the NCI CTCAE version 5.0 or higher. Shift tables from baseline to the worst values will be constructed for laboratory parameters. Individual platelet and absolute neutrophil count (ANC) profiles will be generated for each dose level. Mean values over time for platelets and ANC will be produced for each phase as appropriate.

7.12.3 Vital Signs

Descriptive statistics for vital sign results (diastolic and systolic blood pressure, heart rate, pulse rate and body weight) will be summarized as follows:

- Baseline value (C1D1 or screening if C1D1 is not available).
- Minimum post-baseline value.
- Change to Minimum post-baseline value.
- Maximum post-baseline value.
- Change to Maximum post-baseline value.

Changes to the minimum and maximum post-baseline values will be calculated relative to the baseline value.

For blood pressure values collected during the infusion (every 30 minutes), the number and percentage of patients with changes from pre-infusion blood pressure values will be summarized in the following categories:

- Increase of diastolic blood pressure of at least 10 mm Hg during any infusion.
- Decrease of diastolic blood pressure of at least 10 mm Hg during any infusion.
- Increase of systolic blood pressure of at least 20 mm Hg during any infusion.
- Decrease of systolic blood pressure of at least 20 mm Hg during any infusion.

7.12.4 12-Lead ECGs

ECG data (ventricular rate, RR interval, PR interval, QT interval, and QTcF interval) will be summarized as follows:

- Baseline value (C1D1 or screening if C1D1 is not available).
- Minimum post-baseline value.
- Change to Minimum post-baseline value.
- Maximum post-baseline value.
- Change to Maximum post-baseline value.

Changes to the minimum and maximum post-baseline values will be calculated relative to the baseline value.

In addition, a categorical analysis of QTcF intervals will be performed for each time point. The number and percentage of patients in each QTcF interval (<450 msec, 450-480 msec, >480- <500 msec, and ≥ 500 msec) will be summarized at baseline and each of the subsequent time points. Categories of changes from baseline (≥ 30 msec and ≥ 60 msec) will be summarized as well.

[figure not shown]

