8.0 STUDY DRUG

8.1 Study Drug Administration

All protocol-specific criteria for administration of study drug must be met and documented before drug administration. Study drug will be administered only to eligible patients under the supervision of the investigator or identified subinvestigator(s).

The initial dose should be based on a patient's weight at screening and only adjusted if there is a $\geq 10\%$ change in body weight.

Investigational sites should refer to the pharmacy manual for preparation of each dose. Modakafusp alfa doses < 1.5 mg/kg will be administered over 1 hour (± 10 minutes). Modakafusp alfa doses ≥ 1.5 mg/kg will be administered over 2 hours (± 10 minutes) and could be extended to 4 hours at the investigator's discretion. Any decrease in infusion duration must be discussed with and agreed upon by the sponsor. If a patient presents with an infusion-related reaction at any dose level, the duration of the infusion may be extended per investigator's discretion. Total time from modakafusp alfa dosing solution preparation until end of infusion must not exceed 7 hours.

In the combination treatment cohorts, the recommended pembrolizumab dose of 400 mg will be administered as an IV infusion over 30 ± 10 minutes Q6W in combination with modakafusp alfa. Please see premedication and observation guidelines in Section 8.8.1.

Pembrolizumab will be administered before modakafusp alfa on days when both modakafusp alfa and pembrolizumab are given. At least 30 minutes should elapse between the completion of the infusion of the first study drug and the initiation of the infusion of the second study drug.

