9.3.7 Vital Signs

Vital signs include temperature, pulse, respiratory rate, and oxygen saturation. They include also supine, semirecumbent, or seated measurements of diastolic and systolic blood pressure (after 3 to 5 minutes in this position; all subsequent measurements should be performed in the same initial position). Vital signs will be measured at the times specified in [Appendix A](#).

Blood pressure will be measured every 30 minutes (± 5 minutes) during the first 4 infusions, after the end of the infusion, and at any moment if the patient complains of symptoms consistent with IRR. If the patient experiences hypotension (with or without symptoms) intensive blood pressure monitoring according to local practice should be instituted. The patient cannot be released from the site until blood pressure has returned to Grade 1 or baseline for at least 1 hour.

Any vital sign value that is judged by the investigator as clinically significant will be recorded both in the source documentation and the eCRF as an AE and monitored as described in Section 10.2.

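### The any-infusion blood-pressure percentages in SAP 7.12.3 are expected to step up between 0.75 and 1.5 mg/kg with no drug effect, because planned infusions double in length there

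*SAP*

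**What the plan says.** SAP 7.12.3 defines four in-infusion categories, each measured against the pre-infusion value: a rise or fall of at least 10 mm Hg diastolic, and a rise or fall of at least 20 mm Hg systolic. The first reads "Increase of diastolic blood pressure of at least 10 mm Hg during any infusion". A patient is counted once, however many readings were taken. SAP 7.2.1 gives escalation results one column per dose level.

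Protocol 8.1 ties infusion time to dose. Modakafusp alfa doses below "1.5 mg/kg will be administered over 1 hour"; doses at or above "1.5 mg/kg will be administered over 2 hours". The tolerance is 10 minutes either way. The longer infusion "could be extended to 4 hours" at the investigator's discretion. After an infusion-related reaction at any dose level, "the duration of the infusion may be extended per" the investigator's discretion.

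Protocol 9.3.7 sets readings every 30 minutes, with a tolerance of 5 minutes either way. They apply "during the first 4 infusions, after the end of the infusion, and at any moment if the patient complains of symptoms consistent with IRR".

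SAP 7.12.3 gives no common time window, no count of readings and no allowance for infusion length. By contrast, SAP 7.12.4 tabulates QTcF categories at each time point, and SAP 7.12.2 summarises laboratory results by scheduled time point.

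**The concern.** The chance of being flagged at least once grows with the number of readings. Planned infusion length is set by dose, so the number of readings is too. The columns for 0.1 to 0.75 mg/kg and those for 1.5 to 6 mg/kg are therefore not on the same footing, and the second group is expected to show higher percentages with no drug effect.

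The number of infusions received, from 1 to 4 within the monitored period, is a second source of unequal counts. Lengthening an infusion after a reaction is a third: the number of readings can then depend partly on the event being described.

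What is at stake is how a safety table is read. SAP Appendix A lists these same four categories as clinically relevant changes, so a reader may take a higher percentage from 1.5 mg/kg as haemodynamic effect when part of it reflects more frequent observation.

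**Working it through.** The plan states no expected figure for this table, so there is nothing to reproduce. The check has three steps.

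**1. Scheduled readings per infusion.** Readings = duration ÷ 30 minutes. Whether the reading at the end of infusion counts as during it is not settled, so both counts are shown.

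| Planned duration | Dose levels | End reading counted | Not counted |
|---|---|---|---|
| 1 hour | 0.1, 0.2, 0.4, 0.75 mg/kg | 60/30 = 2 | 1 |
| 2 hours | 1.5, 3, 6 mg/kg | 120/30 = 4 | 3 |

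The ratio is 4/2 = 2 or 3/1 = 3.

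**2. Independent readings, no drug effect.** With the same chance p per reading at every dose, P(flagged) = 1 − (1 − p)^k, where k is the patient's total number of readings. The only exposure figure in the documents is a median of 2 cycles (Protocol 4.3.2.2, 17 patients). Two infusions with the end reading counted give k = 4 at 1 hour and k = 8 at 2 hours. The documents do not give p, so a range is assumed.

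| p (assumed) | 1 hour, k = 4 | 2 hours, k = 8 |
|---|---|---|
| 0.02 | 7.8% | 14.9% |
| 0.05 | 1 − 0.95^4 = 18.5% | 1 − 0.95^8 = 33.7% |
| 0.10 | 34.4% | 57.0% |

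**3. Correlated readings.** Successive readings in one patient are not independent and share one pre-infusion value. I simulated a constant mean with first-order autoregressive readings, an assumed diastolic SD of 5 mm Hg and an assumed correlation of 0.3 to 0.6 between 30-minute readings. A flag is any reading at least 10 mm Hg above the pre-infusion value. Infusions were treated as independent, so the two-infusion figure is 1 − (1 − single-infusion figure)².

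| End reading counted | 1 hour | 2 hours |
|---|---|---|
| One infusion | 4.6–9.8% | 11.3–17.8% |
| Two infusions | 1 − 0.954² = 9.0% to 1 − 0.902² = 18.6% | 1 − 0.887² = 21.3% to 1 − 0.822² = 32.4% |

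The lower end of each range belongs to correlation 0.6 and the upper end to 0.3. Without the end reading, the two-infusion ranges are 2.6–8.9% and 15.5–26.3%. With SD 5, 7 or 9 mm Hg and correlation 0, 0.5 or 0.8, the 2-hour figure exceeded the 1-hour figure in all nine combinations.

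**Comparison at a matched time point.** At, say, 30 minutes into infusion 1, every dose has k = 1, so the no-effect expectation is the same p in every column. The imbalance disappears.

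**The case against.** A reader might infer a false dose-response across the whole range. The documents do not support that. The four lower levels share the 1-hour plan and the three upper levels share the 2-hour plan, so the schedule produces one step. Any further rise depends on extension, which is discretionary.

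A reader might also quote a contrast of 4-fold or more in readings (8 against 2 with the end reading counted), or use four infusions, which under the same assumptions gives about 17–34% against 38–54%. The first needs infusions actually extended to 4 hours. The second needs all four monitored infusions, when the reported median was 2 cycles.

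Symptom-triggered readings may look like a further bias. SAP 7.12.3 describes the values as those taken every 30 minutes during infusion, which most naturally means scheduled readings. The text could say so outright, but it does not clearly admit the triggered ones.

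The consequence is limited. Escalation follows dose-limiting toxicities through the Bayesian model (Protocol 8.3, SAP 7.1). Infusion-related reactions are tabulated directly as events of special interest (SAP 7.12.1), and exposure and infusion changes are reported under SAP 7.8. Expansion is presented by cohort, so the issue lies in the escalation phase, planned at about 30 patients. With about 3 patients per initial cohort, a gap of 12 to 14 percentage points is about 0.4 of a patient (3 × 0.12 to 3 × 0.14), so an individual cohort may not show it.

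Incidence over the regimen as given is also a legitimate safety summary. Replacing it with the first hour of the first infusion would miss reactions in later cycles, and the 60-minute reading falls at or after the end of a 1-hour infusion.

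All of this stands. It limits the weight of the point. It does not make the columns on either side of 1.5 mg/kg comparable.

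**Conclusion.** The point holds as a matter of presentation. The direction follows from the documents alone: 2 to 3 times as many scheduled readings per infusion from 1.5 mg/kg, and hence a higher expected ever-crossed percentage there with no drug effect. The same reasoning applies to all four categories.

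The size does not follow from the documents, which give no blood-pressure variability and no per-reading rate. About 9–19% against 21–32% for a diastolic rise rests on the assumed SD of 5 mm Hg, correlation of 0.3 to 0.6, two independent infusions and the end reading counted.

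The table is descriptive. No primary endpoint, sample size or dose decision depends on it, and a reader should not infer that it would mislead the escalation.

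**What to change.** In SAP 7.12.3:

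- Keep the any-infusion percentages, and state that only scheduled readings count and whether the end-of-infusion reading is included.
- Beside them, show for each dose level the number of in-infusion readings, the number of monitored infusions and the infusion duration.
- Add the same four categories by infusion number and scheduled time since start of infusion (30 minutes, 60 minutes and so on), with the number of patients read at each point.
- Make between-dose comparisons at matching time points.

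The cost is SAP wording and one extra table. No new data are needed, and no dose, infusion time or monitoring changes. The limitation is that time points after the first hour exist only for longer infusions, so matched comparisons do not cover late changes. The retained any-infusion table still shows those.

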7.12.5 Other Observations Related to Safety

Shifts from baseline to the worst post-baseline ECOG score will be tabulated.

7.13

Table 7.2

7.14 Changes in the Statistical Analysis Plan

See Section 1.2 for summary of changes.

Appendix A By-Subject Listings

In addition to the analysis outputs outlined above in the main text, separate by-patient listings will also be generated to include the following information:

- Disposition (date of first dose, date of last dose, number of cycles, reason for discontinuation of study treatment).
- Analysis populations.
- Significant protocol deviations.
- Demographics and Baseline characteristics
- Disease characteristics
- Medical history and Concomitant medical conditions
- Medication history and Concomitant Medication
- Prior therapies
- Study drug exposure.
- TEAEs.
- TEAEs leading to study drug discontinuation.
- TEAEs resulting in dose modifications (delay, interruption, or reduction).
- Grade 3 or higher TEAEs.
- Vitals signs for those patients with clinically relevant changes in blood pressure during the infusion:
 - Increase of diastolic blood pressure of at least 10 mm Hg during any infusion.
 - Decrease of diastolic blood pressure of at least 10 mm Hg during any infusion.
 - Increase of systolic blood pressure of at least 20 mm Hg during any infusion.
 - Decrease of systolic blood pressure of at least 20 mm Hg during any infusion.
- Serious AEs.
- Lab measurements.
- Vital signs
- All deaths
- On-study death
- DLTs during Cycle 1 in dose escalation and expansion safety lead-in.
- Pharmacokinetic concentrations.

- Pharmacokinetic parameters.
- ADA.
- Efficacy (response assessments by mRECIST v1.1 and iRECIST criteria, best overall response, sum of target lesion diameter, status of non-target lesion, status of new lesion, all time to events).

Appendix B Date Imputation Rules

Incomplete Dates in the Screening Period

1. If only the day-component is missing, the first day of the month will be used if the year and the month are the same as those for the first dose of study drug. Otherwise, the fifteenth will be used.
2. If only the year is present, and it is the same as the year of the first dose of study drug, the fifteenth of January will be used unless it is later than the first dose, in which case the date of the first of January will be used.
3. If only the year is present, and it is not the same as the year of the first dose of study drug, the fifteenth of June will be used.

Incomplete Adverse Event Onset Date

Assumption: For on-study Adverse Events.

If *year* is missing (or completely missing): set to the date of first dose.

If (*year* is present and *month* and *day* are missing) or (*year* and *day* are present and *month* is missing):

If *year* = year of first dose: set the date to the first dose date.

If *year* < year of first dose: set *month* and *day* to December 31st.

If *year* > year of first dose: set *month* and *day* to January 1st.

If *month* and *year* are present and *day* is missing:

If *year* = year of first dose, and:

If *month* = month of first dose: set *day* to day of first dose.

If *month* < month of first dose: set *day* to last day of *month*.

If *month* > month of first dose: set *day* to 1st day of *month*.

If *year* < year of first dose: set *day* to last day of month.

If *year* > year of first dose: set *day* to 1st day of month.

For all other cases: set to date of first dose.

Incomplete Adverse Event Resolution Date

Assumption: For on-study Adverse Events

If *day* is missing but *month* and *year* are non-missing, impute as the earliest of:

Last day of the *month*

Date cutoff date

Death date

If *day* is missing but *month* and *year* are non-missing, impute as the earliest of:

December 31st

Date cutoff date

Death date

Incomplete Concomitant Medication Start Date/Prior Therapy Start Date/Progression Date during Prior Anti-Cancer Therapy

If *year* is missing (or completely missing): do not impute.

If (*year* is present and *month* and *day* are missing) or (*year* and *day* are present and *month* is missing):

Set *month* and *day* to January 1st.

If *year* and *month* are present and *day* is missing:

Set *day* to 1st day of month.

Incomplete Concomitant Medication End Date

If *year* is missing (or completely missing): do not impute.

If (*year* is present and *month* and *day* are missing) or (*year* and *day* are present and *month* is missing):

Set *month* and *day* to December 31st.

If *year* and *month* are present and *day* is missing:

Set *day* to last day of the month.

Incomplete Subsequent Anti-Cancer Therapy Start Date

If *year* is missing (or completely missing): set to date of last dose of study treatment + 1

If (*year* is present and *month* and *day* are missing) or (*year* and *day* are present and *month* is missing):

If *year* > year of the last dose: Set *month* and *day* to January 1st.

If *year* = year of the last dose: Set *month* and *day* to date of last dose of study treatment +1.

If *year* and *month* are present and *day* is missing:

Set *day* to 1st day of month if the resulting imputed date is greater than date of last dose.

Otherwise set the imputed date to date of last dose + 1.

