10.3 Monitoring of AEs and Period of Observation

AEs, both nonserious and serious, will be monitored throughout the study as follows:

- AEs will be reported from the signing of informed consent through 30 days after administration of the last dose of study drug or the start of subsequent anticancer therapy, whichever occurs first, and recorded in the eCRFs. The reporting period for irAEs (Section 8.6.3.2) is extended to 90 days after administration of the last dose of study drug or the start of subsequent anticancer therapy, whichever occurs first, and recorded in the eCRFs.
- SAEs will be reported to the Takeda Global Pharmacovigilance department or designee from the signing of informed consent through 30 days after administration of the last dose of study drug, even if the patient starts nonprotocol therapy, and recorded in the eCRF. The reporting period for serious irAEs is extended to 90 days after administration of the last dose of study drug. After this period, only related SAEs must be reported to the Takeda Global Pharmacovigilance department or designee. SAEs should be monitored until they are resolved or are clearly determined to be caused by a patient's stable or chronic condition or intercurrent illness(es).

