7.12 Safety Analysis

7.12.1 Adverse Events

Adverse events will be coded using the Medical Dictionary for Regulatory Activities (MedDRA) Version 23.0 or later (based on version at time of database lock). Treatment-emergent is defined as any AE that occurs on or after the date of the first dose of any study treatment through 30 days after the last dose of any study treatment.

Treatment-emergent AEs will be summarized by MedDRA system organ class (SOC), and preferred term. For summary tabulations the following hematologic abnormalities coded to MedDRA preferred terms in the Investigations SOC will be pooled with the appropriate clinical terms in the blood and lymphatic system disorders SOC:

MedDRA Preferred Term (Investigation SOC)	Mapped to (Blood and lymphatic system disorders SOC)
Neutrophil count decreased	Neutropenia
Platelet count decreased	Thrombocytopenia
Hemoglobin decreased	Anemia
White blood cell count decreased	Leukopenia

Treatment-emergent AEs will also be summarized by the National Cancer Institute Common Terminology Criteria for Adverse Events (NCI CTCAE) version 5.0.

Summary tabulations will include the following categories:

- Treatment-emergent AEs.
- Drug-related treatment-emergent AEs.
- Grade 3 or higher treatment-emergent AEs.
- Grade 3 or higher drug-related treatment-emergent AEs.
- Grade 3 and Grade 4 TEAEs (based on maximum severity).
- Grade 3 and Grade 4 drug-related TEAEs (based on maximum severity).
- The most commonly reported treatment-emergent AEs (i.e., those events reported by $\geq 10\%$ of all patients in each phase or overall population as appropriate).
- Serious treatment-emergent AEs.
- Drug-related serious treatment-emergent AEs.
- Treatment-emergent AEs resulting in discontinuation of study drug.
- Treatment-emergent AEs resulting in study drug modifications (including discontinuation, delay, reduction, and interruption).

- Treatment-emergent AEs resulting in dose delays.
- Treatment-emergent AEs resulting in dose reductions.
- Treatment-emergent AEs resulting in dose interruptions.
- TEAEs leading to death
- Treatment emergent AESI – all grades
- Treatment emergent AESI grade 3 and above
- Treatment emergent AESI grade 3 or 4
- Treatment-emergent AEs resulting in infusion rate reductions.
- Treatment-emergent AEs resulting in infusion interruptions.
- Serious treatment emergent AESI

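### SAP Appendix B imputes incomplete AE onsets to the first-dose date without checking a known end date, so an AE that ended in screening can be counted as treatment-emergent

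*SAP*

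**What the plan says.** SAP section 7.2.3 sends all handling of incomplete dates to Appendix B. For AE onset, four branches there return the date of first dose:

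- Day missing, same month and year as first dose: "If *month* = month of first dose: set *day* to day of first dose".
- Month missing, same year: "If *year* = year of first dose: set the date to the first dose date".
- Year or whole date missing: "If *year* is missing (or completely missing): set to the date of first dose".
- The default: "For all other cases: set to date of first dose".

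None refers to the resolution date. The block is headed "Assumption: For on-study Adverse Events", a term the SAP does not define for AEs.

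Appendix B opens with a different block for incomplete dates in the screening period. If only the day is missing and month and year match first dose, it uses the first of the month. If only the year is known and matches, it uses 15 January, or 1 January if the 15th falls after first dose.

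Protocol section 10.3 collects events from consent: "AEs will be reported from the signing of informed consent through 30 days after administration of the last dose". SAP section 7.12.1 defines treatment-emergent as "any AE that occurs on or after the date of the first dose of any study treatment", through 30 days after the last dose.

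For AE resolution dates, the condition "If *day* is missing but *month* and *year* are non-missing, impute as the earliest of" is printed twice in succession. The first copy leads to the last day of the month and the second to 31 December, each capped by cutoff or death.

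**The concern.** Defaulting an unknown onset to first dose is a common cautious choice when nothing else is known. The difficulty arises when something else is known. If the record shows that the event ended before dosing, the rule overrides that fact and produces an onset after the event's own end. Taken at face value, the imputed date then makes a pretreatment event treatment-emergent.

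Frequency and severity of TEAEs is a primary endpoint in phase 1b and in the phase 2 safety lead-in (SAP section 5.1). Summaries are by dose level, with cohorts of about 3 patients and a lead-in of 3 to 9, so a single misclassified event is visible in its row.

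The duplicated resolution condition is a separate and smaller matter: one input has two stated outputs, and an end date with only the year known has no rule.

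**Working it through.** The plan states no figure to reproduce, so the check applies the rules as written.

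**Worked case.** First dose 20 March 2022, known resolution 10 March 2022, so the event is certainly pre-dose.

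| Recorded onset | AE onset block | Screening-period block |
|---|---|---|
| March 2022, day missing | 20 March (after the event's end) | 1 March |
| 2022 only | 20 March (after the event's end) | 15 January |
| Entirely missing | 20 March (after the event's end) | no rule |
| February 2022, day missing | 28 February | 15 February |

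In the first three rows the AE block gives an onset 10 days after the event ended, on the first-dose date, hence a TEAE. In rows 1 and 2 the screening block gives a pre-dose date. The two blocks conflict, and no text ranks them. The last row causes no trouble under either.

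**How often the rule bites, given such an event.** Inputs: a screening window of 21 days (Protocol section 9.3) and, as an assumption, 2022 as the calendar year. Take every first-dose date (365), every onset k = 1 to 21 days before dose, and every known end from onset to the day before dose (k choices). That gives 365 × (1 + 2 + … + 21) = 365 × 231 = 84,315 combinations, weighted equally.

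- Day missing: 44,583 / 84,315 = 52.9% imputed to first dose.
- Month and day missing: 81,004 / 84,315 = 96.1%. The exceptions are onsets in the previous calendar year.
- Date entirely missing: 84,315 / 84,315 = 100%.

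Hand check of the first figure with a 30-day month and first-dose day d. The combinations with onset in the dosing month number 1 + 2 + … + min(d − 1, 21). Summing over d = 1 to 22 gives 21 × 22 × 23 / 6 = 1,771, and d = 23 to 30 gives 8 × 231 = 1,848. Then (1,771 + 1,848) / (30 × 231) = 3,619 / 6,930 = 52.2%, close to the calendar result.

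**After capping onset at the known end date.** All three patterns give 0 false TEAEs, because the capped onset is never later than an end that precedes dosing.

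**Resolution dates.** For the same day-missing input, the two copies differ by 334 days for January, 275 for March, 184 for June, 31 for November and 0 for December, unless cutoff or death falls on or before the end of the month.

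**The case against.** The best counter-argument is one of scope. The AE block is limited to on-study events. The only on-study term the SAP defines, on-study death in section 7.12.1, starts at first dose. Protocol section 10.1.1 treats an event between consent and first dose as a pretreatment event. On that reading a screening event belongs to the screening-period block and is not counted. In addition, section 7.12.1 speaks of when an AE occurs and does not say that the imputed onset alone sets the flag. Protocol section 12.1 also provides logic checks and site queries for missing and inconsistent dates.

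Part of this stands. The SAP does not instruct anyone to misclassify an event, and queries should make the situation uncommon. But the scope argument does not settle the matter. The AE onset block has branches for months and years before first dose, so it plainly expects pre-dose onsets. Protocol section 10.3 calls events from consent AEs. Nothing says the screening block overrides the AE block, or how a screening AE is recognised when its onset is incomplete. What the argument does show is that two rules compete.

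On the resolution condition, the second copy is almost certainly a slip. The concomitant-medication end-date rule in the same appendix assigns 31 December when year is present and month and day are missing. The planned AE outputs in section 7.12.1 contain no AE duration or time-to-resolution analysis.

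**Conclusion.** The point holds as a minor defect of specification. Appendix B can turn an AE known to have ended before dosing into a TEAE, and it contains a competing rule with the opposite result and no order of precedence.

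Its size is probably small. It needs a screening AE, an onset still incomplete after queries, and a recorded end before first dose. The documents give no frequency for that combination. The 52.9%, 96.1% and 100% are shares of equally weighted date combinations among such events, not rates to expect in the trial.

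Three stronger readings are tempting but unsupported:

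- A reader might infer that about 63% of these events would be misclassified. That figure, (231 + 8 × 21) / (30 × 21) = 399 / 630, is the share of all screening onsets falling in the first-dose month. Events known to have ended before dosing lean towards earlier onsets when all date combinations are weighted equally, which gives the lower share.
- A reader might infer that the primary TEAE rate is materially inflated. Protocol section 4.3.2.2 reports that 17 of 17 patients already had a TEAE at the January 2021 cutoff, so at that level the any-TEAE row could not move. Only preferred-term, grade or serious-TEAE rows could. There, one patient is 1/9 = 11% to 1/3 = 33% of a 3-to-9-patient lead-in, but that is true of any miscounted patient and says nothing about how often this rule errs. The error is towards over-counting toxicity.
- A reader might infer that the duplicated resolution condition alters a primary result. No planned primary analysis is shown to use an imputed resolution date. The effect is confined to listings.

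**What to change.** Add to the AE onset block: *If a known resolution date precedes the imputed onset, set onset to the resolution date. An AE whose known resolution date is before first dose is not treatment-emergent. This takes precedence over the other incomplete-date rules for AEs collected from consent.* A known date here should mean a recorded one, not one that is itself imputed.

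As a text correction, change the second resolution condition to: *If day and month are missing but year is non-missing*. That matches the form of the concomitant-medication end-date rule, removes the overlap and covers the year-only case.

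The cost is a few lines in the SAP and one comparison in the AE derivation program. Neither change touches conduct, dosing or sample size. Both should be made before database lock.
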